7.9.6.2 Performance Requirements and Endpoint Definition

Performance requirements are not pre-specified for this objective. The endpoint is the amount of pacing for asystole the subject received.

7.9.6.3 Rationale for Performance Criteria

This objective is for the purpose of characterizing prevalence of need for asystole pacing in this population. There are no pre-specified performance criteria.

7.9.6.4 Analysis Methods

The CIP Section 8.6 specifies the programming requirements and recommendation at the pre-hospital discharge visit, where the requirements on pause prevention is for asystole pacing. Descriptive statistics will be used to summarize the number of subjects and amount of asystole pacing experienced during follow-up.

7.9.6.5 Determination of Subjects/Data for Analysis

All subjects successfully implanted with an EV ICD with at least one device interrogation post-implant will be eligible for the analysis. At minimum, all instances occurring on or before the date at which all implanted subjects have had the opportunity to be followed for 6 months post-implant will be included.

7.9.7 Ancillary Objective #5: ATP Performance

Summarize ATP performance with spontaneous arrhythmias.

7.9.7.1 Hypothesis

There are no hypotheses for this objective, as the purpose is to characterize defibrillation performance through use of ATP.

7.9.7.2 Performance Requirements and Endpoint Definition

Performance requirements are not pre-specified for this objective. The endpoint is defined as whether a spontaneous ventricular tachycardia episode for which ATP was delivered by the EV ICD was terminated by ATP. Spontaneous arrhythmias will be adjudicated to determine the underlying rhythm and whether they were terminated by ATP.

7.9.7.3 Rationale for Performance Criteria

It is projected that only a small subset of implanted subjects may experience one or more ventricular arrhythmias during follow-up. Therefore, device performance regarding such episodes will be characterized only. There are no pre-specified performance criteria.

7.9.7.4 Analysis Methods

Results will be summarized in aggregate using descriptive statistics. All monomorphic and polymorphic ventricular arrhythmias with EGM will be partitioned by whether the treated rhythm received ATP and/or shock, whether it successfully terminated as a result, and by the specific rhythm of the episode (monomorphic vs. polymorphic VT/VF). Both the number of episodes and the number of subjects experiencing such episodes will be reported. The percentage of monomorphic VT episodes successfully terminated by ATP and its 95% confidence interval will be estimated using the Generalized Estimating Equations (GEE) method.

7.9.7.5 Determination of Subjects/Data for Analysis

All subjects successfully implanted with an EV ICD having at least one device interrogation post-implant will be included in the analysis. At minimum, all VT/VF episodes occurring on or prior to the date by which all implanted subjects have had the opportunity to be followed for 6 months post-implant will be included in the analysis.

7.9.8 Ancillary Objective #6: Adverse Events

Summarize adverse events.

7.9.8.1 Hypothesis

There are no hypotheses for this objective, as safety of the EV ICD System is being evaluated by Primary Objective #1 (see section 7.9.1). This objective is to provide a comprehensive summary of adverse events experienced during follow-up.

7.9.8.2 Performance Requirements and Endpoint Definition

Performance requirements are not pre-specified for this objective. The endpoint is an adverse event (see CIP Table 12 for definition of adverse event) experienced by a subject post-enrollment and prior to exit. Adverse events will be adjudicated by a Clinical Events Committee (CEC) for relatedness to the EV ICD System and procedure.

7.9.8.3 Rationale for Performance Criteria

This objective is for the purpose of gathering comprehensive data pertaining to subject health over at least the first six months post-implant. There are no pre-specified performance criteria.

7.9.8.4 Analysis Methods

Results will be summarized in aggregate using descriptive statistics. Counts and percentages of subjects experiencing system and/or procedure-related adverse events will be reported, as well as, in the case of system-related events, the specific component of the system to which the event was related. Adverse Events will be broken out by MedDRA keyterm, with both counts of events and counts of subjects experiencing each type of event reported. The seriousness of adverse events and adverse device effects will also be summarized. Details of individual adverse events including MedDRA key term, center diagnosis, description, actions, outcome, relatedness and seriousness will be listed. When deemed necessary, individual adverse events where center investigator classification on relatedness differs from the CEC adjudication and/or center investigator assessment on seriousness differs from the Medtronic Safety assessment will be identified for reporting. Determination of Subjects/Data for Analysis

All subjects for whom an implant of the investigational product is attempted will be included in the analysis. At minimum, all adverse events recorded by the date by which all implanted subjects have been followed at least 6 months post-implant will be included.

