Table 28 provides examples of adverse events associated with the use of transvenous ICD systems reported in three previous Medtronic studies. These three predicate studies were selected as a reference for EV ICD performance as they were contemporary and used adverse event definitions consistent with those utilized in the EV ICD Pivotal Study. The three predicate Medtronic studies include BLOCK HF, REVERSE, and Evera MRI. These studies collected adverse event data from 1035 subjects that underwent an ICD implant. The average follow-up time exceeded 9 months in all three trials. Table 28 displays the adverse event rates classified as related to the implanted system and/or procedure. To characterize the safety profile of a single lead ICD system, all adverse events related to an atrial or left ventricular pacing lead were excluded from consideration. Kaplan-Meier estimates and associated 95% confidence intervals of the adverse event rates are provided in the Table below at 30-days and 12-months (365 days) post-implant to characterize both peri-procedural and long-term adverse events related to the procedure or implanted system.

EV ICD Pivotal Study Clinical Investigation Plan

MDT16028

Version 1.0, 02-JUL-2019

Page 148 of 165

Table 28: System and/or Procedure Related AEs Associated with Transvenous ICD Systems (n=1035)

MedDRA Preferred Term	Within 30-days of Implant		Within 12-months of Implant	
	No. Events (No. Subjects, %)	95% CI	No. Events (No. Subjects, %)	95% CI
ACUTE PULMONARY OEDEMA	2 (2, 0.19%)	0.05% - 0.77%	2 (2, 0.19%)	0.05% - 0.77%
ADVERSE DRUG REACTION	5 (5, 0.39%)	0.15% - 1.03%	5 (5, 0.39%)	0.15% - 1.03%
ANGINA UNSTABLE	1 (1, 0.10%)	0.01% - 0.68%	1 (1, 0.10%)	0.01% - 0.68%
ANXIETY	0 (0, 0%)	--	1 (1, 0.13%)	0.02% - 0.93%
ARRHYTHMIA SUPRAVENTRICULAR	1 (1, 0.10%)	0.01% - 0.68%	2 (1, 0.10%)	0.01% - 0.68%
ATELECTASIS	3 (3, 0.29%)	0.09% - 0.90%	3 (3, 0.29%)	0.09% - 0.90%
ATRIAL FIBRILLATION	8 (7, 0.68%)	0.32% - 1.41%	8 (7, 0.68%)	0.32% - 1.41%
ATRIAL FLUTTER	1 (1, 0.10%)	0.01% - 0.68%	1 (1, 0.10%)	0.01% - 0.68%
ATRIAL THROMBOSIS	0 (0, 0%)	--	1 (1, 0.10%)	0.01% - 0.74%
ATRIOVENTRICULAR BLOCK COMPLETE	3 (2, 0.19%)	0.05% - 0.77%	3 (2, 0.19%)	0.05% - 0.77%
ATRIOVENTRICULAR BLOCK THIRD DEGREE	6 (6, 0.58%)	0.26% - 1.29%	6 (6, 0.58%)	0.26% - 1.29%
BACTERAEMIA	0 (0, 0%)	--	1 (1, 0.10%)	0.01% - 0.71%
BODY TEMPERATURE INCREASED	1 (1, 0.10%)	0.01% - 0.68%	1 (1, 0.10%)	0.01% - 0.68%
BRADYCARDIA	2 (2, 0.19%)	0.05% - 0.77%	2 (2, 0.19%)	0.05% - 0.77%

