9.1 Analysis for Market Approval Outside the US

Human clinical data may be needed to support marketing applications in CE Mark countries and other geographies outside the US. Therefore, Medtronic plans to analyze the accumulated data once 60 subjects undergoing implant of the EV ICD System have completed their 3-month follow-up visit. This analysis will include characterizing both defibrillation efficacy at implant and incidence of major EV ICD System/procedure-related complications through at least 3 months. All subjects will continue to be followed and the timeline for other marketing applications will not be impacted by this analysis. This analysis will not utilize an alpha-spending function. Medtronic also plans to submit updated data from the ASD2 feasibility study and the ongoing EV ICD Pilot study for further information regarding defibrillation testing and safety.

In the EV ICD Pivotal interim report for CE Mark submission, the definitions of EV ICD system/procedure-related major complications and defibrillation testing success at implant are the same as those for the primary safety and efficacy objectives of the study. The safety endpoint (major EV ICD System/procedure-related complications) will be characterized descriptively through 3 months. The defibrillation efficacy endpoint will be characterized using descriptive statistics such as frequency and percentage. No performance goal or hypothesis testing is planned for either endpoint. When the 60-patient sample size was determined, it was expected that by the time 60 patients have completed 3 months of follow-up approximately 171 subjects would have undergone the defibrillation testing and 131 subjects would have completed at least one month of follow-up.

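### Related adverse events are summarized as percentages with no time horizon over unequal follow-up, in a different form from the protocol's 30-day and 12-month Kaplan-Meier reference rates

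*SAP*

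**What the plan says.** **Statistic.** SAP 7.9.8.4 (matching CIP 12.11.4) plans that "Counts and percentages of subjects experiencing system and/or procedure-related adverse events will be reported", with counts of events and of subjects by MedDRA term. It names no horizon, person-time rate or time-to-event method.

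**Denominator.** "All subjects for whom an implant of the investigational product is attempted will be included in the analysis". Unsuccessful implants are therefore counted.

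**Data cut.** The minimum is "all adverse events recorded by the date by which all implanted subjects have been followed at least 6 months post-implant".

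**Exposure.** SAP section 5 expects enrollment to take about 15 months. SAP 7.11 reports that enrollment was paused on 20 March 2020, about six months after the first enrollment, with 25 implant attempts by 27 March 2020. CIP 8.5.8 and 8.19 allow a subject with an unsuccessful implant to exit after 30 days or once related events have resolved.

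**Reference rates.** CIP Appendix E presents three earlier transvenous ICD studies as a reference for the device's performance: "Kaplan-Meier estimates and associated 95% confidence intervals of the adverse event rates are provided in the Table below at 30-days and 12-months". The appendix says this information may help in judging whether an event is unexpected.

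**Major complications.** These already have a fixed horizon: a 182-day Kaplan-Meier rate in SAP 7.9.1.4 and a curve over time in the CIP synopsis.

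**The concern.** A crude percentage is interpretable when every subject is observed for the same time. Here the cut is a calendar date, so early enrollees contribute far more time at risk than late ones, and failed implants contribute very little. Two trials of the same device with the same risk would report different percentages if one enrolled faster.

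The nearest benchmark in the plan, Table 28, is given at 30 days and 365 days by Kaplan-Meier. The planned percentage shares neither the horizon nor the estimator. What is at stake is how the related adverse-event profile is read, above all for events that accrue late. CIP 9.3 names such a risk itself: lead dislodgment during chronic substernal implantation.

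**Working it through.** **1. Follow-up at the minimum cut.** Take uniform enrollment over A months (an assumption) and a cut 6 months after the last implant. Potential follow-up then runs from 6 to 6 + A months. For A = 15 the range is 6 to 21, the mean is 6 + 15/2 = 13.5 months, and the share with at least 12 months is (21 − 12)/15 = 60%.

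**2. Inputs from SAP 6.1.** Both curves are Weibull, S(t) = exp(−λ·t^k), with t in months.
- Major complications, 90% free at 1 month and 86% at 6 months: λ = −ln 0.90 = 0.1054; k = ln(ln 0.86 / ln 0.90) / ln 6 = 0.200.
- Attrition, 9% at 1 month and 16% at 12 months: λ = −ln 0.91 = 0.0943; k = ln(ln 0.84 / ln 0.91) / ln 12 = 0.247. By 6 months this gives 1 − exp(−0.0943 × 6^0.247) = 13.7%.

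The documents give no projected adverse-event percentage to reproduce. As a check on the inputs, simulating the safety sample size with them (292 subjects, log-scale bound, 10,000 runs) gave 89.5% power, against the stated 90%.

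**3. Expected crude percentage.** For potential follow-up f, the chance that a subject is recorded with an event is the integral from 0 to f of S_attrition(t) dF_event(t). Average this over f uniform on (6, 6 + A). Accrual of 9 and 24 months is an assumed bracket around the planned 15.

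| Event type | 9 months | 15 months | 24 months | True value at 1 / 6 / 12 months |
|---|---|---|---|---|
| SAP 6.1 major-complication curve, stated attrition | 14.4% | 14.9% | 15.6% | 10.0 / 14.0 / 15.9% |
| Assumed constant hazard, 5% at 6 months, stated attrition | 7.5% | 9.4% | 12.1% | 0.9 / 5.0 / 9.8% |
| Same event, no attrition | 8.6% | 10.8% | 14.1% | 0.9 / 5.0 / 9.8% |

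For the constant-hazard event, h = −ln(0.95)/6 = 0.00855 per month, so 12-month incidence is 1 − 0.95² = 9.75%. The right-hand column does not change with accrual. The crude columns do.

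**4. Is Table 28 really not crude?** Decreased sensing at 12 months: 2/1035 = 0.19%, listed as 0.28%. Anxiety at 12 months: 1/1035 = 0.10%, listed as 0.13%. The listed values allow for incomplete follow-up.

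**5. Which pattern applies?** Table 28 shows both. Implant site haematoma is early (21 events by 30 days, 23 by 12 months). Lead dislodgement (14, then 20), implant site pain (10, then 19) and inappropriate device therapy (1, then 6) keep accruing.

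**The case against.** The best defense is that nothing inferential depends on this table. Objective #6 has no hypothesis and no performance criterion, and safety is tested by the 182-day Kaplan-Meier rate of the primary objective. On the SAP's own front-loaded curve the drift across accrual periods is 1.2 points (15.6 − 14.4). The larger drift needs a constant-hazard event that the documents do not posit, and ignoring the stated attrition inflates it. All of this stands, and it limits the point to presentation of a descriptive objective.

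A reader might infer more than the documents support:

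- **That comparison with Table 28 is impossible.** Appendix E plans no formal comparison, onset dates are collected (CIP 10.1.1), and SAP section 3 leaves room for further analyses. Comparable figures can be produced; they are just not pre-specified.
- **That every subject has 6 to 21 months.** That range follows from planned enrollment and applies to potential follow-up only. The cut is a minimum, the pause lengthens the upper end, and failed implants and early exits fall below 6 months.
- **That asystole pacing has the same fault.** SAP 7.9.6.4 says "Descriptive statistics will be used to summarize the number of subjects and amount of asystole pacing experienced during follow-up". It plans no percentage, and Appendix E gives no asystole-pacing rate. Only the unequal exposure carries over.
- **That the CE Mark safety figure will be too low.** SAP 9.1 says "The safety endpoint (major EV ICD System/procedure-related complications) will be characterized descriptively through 3 months". It names neither estimator nor denominator. The 171 subjects mentioned there are those expected to have had defibrillation testing, not a stated safety denominator, so no bias can be attributed to it.
- **That the optional Kaplan-Meier curves for shocks in SAP 7.9.3.4 are an error.** The method is already named; making it mandatory is a preference.

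**Conclusion.** The point holds for related adverse events in SAP 7.9.8.4. The percentage pools exposures from about 30 days to 21 months or more, has no horizon, depends on enrollment pace, and is not in the form of the protocol's reference rates.

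The size depends on when events occur. Moving from 9 to 24 months of accrual shifts an early-weighted event by about 1 point, and an assumed constant-hazard event from 7.5% to 12.1%, a factor of about 1.6. At the planned 15 months both crude values (14.9% and 9.4%) lie fairly near the 12-month incidence (15.9% and 9.8%), but that comes from the accrual length and is not a property of the method. These figures rest on uniform accrual, a cut exactly 6 months after the last implant, and attrition independent of the event. The 5% six-month incidence is illustrative.

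No primary conclusion changes. This is a cheap improvement to an ancillary descriptive objective.

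**What to change.** In SAP 7.9.8.4, add Kaplan-Meier (or cumulative incidence) estimates with 95% CI at 30, 182 and 365 days for subjects with system- or procedure-related adverse events, overall and for the MedDRA terms to be read against Table 28. The 30-day and 365-day points match that table, and the 182-day point matches the primary safety horizon. State how exits, deaths and unsuccessful implants are handled, and show the number at risk at each time point. Keep the raw counts and listings. The 365-day estimate is feasible, since about 60% of subjects would have at least 12 months of potential follow-up under 15-month uniform enrollment.

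Optional:
- In SAP 7.9.6.4, report asystole pacing per patient-year of interrogated follow-up.
- In SAP 9.1, name the 90-day Kaplan-Meier estimate and its denominator.

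The cost is a few lines of SAP text and some standard tables from dates already collected. No new data are needed.

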7.9.9 Ancillary Objective #7: Chronic Defibrillation Testing

Characterize the EV ICD defibrillation testing success rate at 6 months post-implant.

7.9.9.1 Hypothesis

No statistical hypotheses will be tested for this objective.

7.9.9.2 Performance Requirements and Endpoint Definition

The performance requirement for this objective is that the observed proportion of subjects, among those with an induced VF episode at their 6-month visit, for whom the episode is successfully terminated with a shock is at least 0.88. The endpoint, defibrillation testing success, is defined as successful completion of the chronic defibrillation testing protocol at the 6-month visit. Subjects included in this analysis should have consented to the chronic defibrillation testing. If a consented chronic defibrillation testing is conducted after the 6-month visit, it will also be included in the analysis.

7.9.9.3 Sample Size

Consecutive subjects at centers that agree with and obtain approval from their EC and associated regulatory authority if applicable will be approached for consent to undergo chronic defibrillation testing (see CIP Addendum for 6-Month Defibrillation Testing) until a minimum of 17 and up to 34 subjects have completed testing. Subjects who have consented to participate in this testing will have their chronic defibrillation testing included in the analysis.

7.9.9.4 Rationale for Performance Criteria

Chronic defibrillation testing is rarely done as standard of care, and places burden on the subject. Therefore, this trial will gather minimal chronic defibrillation testing data to assess efficacy of the EV ICD System in a chronic defib testing, as defined by an observed chronic defibrillation success rate meeting the primary efficacy Objective Performance Criterion of 0.88.

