Medtronic has developed an extravascular ICD system which uses a substernal lead rather than a transvenous or a subcutaneous lead. The EV ICD System has similar capabilities to a single-chamber transvenous system while avoiding leads in the heart or vasculature. Compared to current market-released non-transvenous subcutaneous ICDs, the EV ICD System includes a smaller device that uses less defibrillation energy which may result in longer battery life and has the additional capabilities to deliver pacing therapies such as ATP and backup asystole pacing from a single device.

Previously published case studies indicate defibrillation from non-endocardial locations is possible and shock energies similar to those of transvenous devices can successfully defibrillate if the defibrillation coil is placed in an epicardial or mediastinal location^{8,9,10,14,15,16,17,18,19,20}. The EV ICD System is of similar size and energy outputs as current transvenous systems (e.g., approximately 33cc and 40 Joules).

The first human experience of acute and chronic defibrillation lead placement in the substernal extra-cardiac space was reported by Tung et al. in 2007 using a minimally invasive approach via the manubrium¹⁰. In three patients (two patients having ipsilateral venous occlusion and one patient wishing to avoid additional transvenous hardware placement), either a Medtronic Model 6996SQ or Model 6937 coil was tunneled to the substernal extra-cardiac space anterior to the right ventricle (RV). All implants were successful without complication. Ventricular Fibrillation (VF) was induced with T-wave shock. In each patient, the safety margin was determined to be at least 10 Joules (J) by two successful VF terminations.

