8.5.7. Induction and Defibrillation Testing

To ensure subject safety in an ambulatory setting, sustained shockable ventricular arrhythmia (SSVA) induction and defibrillation testing is required at implant. Adjust device programming to ensure adequate safety margins for sensing and defibrillation during SSVA induction testing.

The testing protocol may require up to six successful SSVA episodes induced and up to 10 EV ICD shocks delivered (Figure 7).

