8.5.7.2. Testing and Programming Defibrillation Therapy

Defibrillation testing success is defined as meeting one of the following criteria:

- a. Single SSVA conversion at 20J, or
- b. Conversion of two consecutive episodes of SSVA at 30J in final system configuration.

Follow the defibrillation testing as outlined in Figure 7, beginning at Episode 1 (20J). The following requirements shall be observed while conducting defibrillation testing:

- Defibrillation at a given energy will be deemed successful if SSVA is terminated, regardless of whether the shock is delivered manually or automatically by device.
- In one of the two consecutive SSVA episodes, up to two 30J shocks are permitted.

- To achieve final system configuration, changing the position of the ICD generator and/or the lead, or changing shock polarity is permitted.
- If the device or lead position are altered (e.g., position changed as part of troubleshooting), defibrillation success must be demonstrated with the new system configuration.
- If defibrillation protocol episodes are not exhausted, remaining episodes may be used on a subsequent day (e.g., next day or during the admission) to complete the defibrillation testing protocol
- For the first episode following the 20J therapy or the first 30J episode following a “Troubleshoot System” step in Figure 7, program Rx1 polarity to either STD or REV, and program Rx2 polarity the opposite of Rx1 polarity.
- If the episode follows a defibrillation success at 30J, and the previous episode had a defibrillation success with Rx1, program Rx1 and Rx2 to the polarity of Rx1 in the previous episode.
- If the episode follows a defibrillation success at 30J, and the previous episode had a defibrillation success with Rx2, program Rx1 to the same polarity as Rx2 in the previous episode and program Rx2 off.

EV ICD Pivotal Study Clinical Investigation Plan

MDT16028

Version 1.0, 02-JUL-2019

Page 60 of 165

Medtronic

[figure not shown]

Figure 7: Diagram outlining the process of SSVA induction and defibrillation testing

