Appendix I: Chronic Defibrillation Testing Protocol

Each subject will be induced to produce up to two episodes of SSVA and allowed two shock attempts to convert each SSVA from the EV ICD, for up to a total of 4 potential shocks from the EV ICD (see Figure 11). Starting therapy polarity is at the discretion of the physician (in the programmed setting).

[figure not shown]

Figure 11: Diagram outlining the process of chronic SSVA induction and defibrillation testing

Episode 1

Program Rx1 and Rx2 therapies as follows:

	Rx1	Rx2
NID	30/40	NA
Redetect NID	NA	9/12
VF Therapy Status	ON	ON
Energy	30J	40J
Pathway	As programmed	As programmed

If Episode 1, Rx1 or Rx2 is successful in terminating the episode, the EV ICD System will have passed chronic defibrillation testing criteria. No additional inductions are required, and it is recommended to leave the system implanted with no changes.

EV ICD Pivotal Study Clinical Investigation Plan

MDT16028

Version 1.0, 02-JUL-2019

Page 161 of 165

Medtronic

Episode 2

	Rx1	Rx2
NID	9/12	NA
Redetect NID	NA	9/12
VF Therapy Status	ON	ON
Energy	40J	40J
Pathway	Opposite of programmed	Opposite of programmed

If Episode 2, Rx1 or Rx2 is successful in terminating the episode, the EV ICD System will have passed chronic defibrillation testing criteria. No additional inductions are required, and it is recommended to leave the system implanted with no changes.

If both Rx1 and Rx2 fail in Episode 2, the EV ICD System will have failed chronic defibrillation testing criteria and the next steps are at the physician's discretion. Medtronic recommends EV ICD device or lead revision (at a minimum), or system removal.

Prior to inducing and throughout the chronic defibrillation protocol, it is recommended to consider the following to improve defibrillation outcome or troubleshooting in the event of failure of first episode(s):

- Check for/resolve high impedance values
- Check for/resolve air in tunnel (e.g., fluoroscopy)
- Check for/resolve gastric bubbles (gas)
- Press on device pocket during testing
- Perform defibrillation during held end tidal expiration (end expiration apnea)

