7.9.2.2 Performance Requirements and Endpoint Definition

Performance requirements for this objective define both the endpoint and the OPC. The endpoint, defibrillation testing success, is defined as:

- Single SSVA conversion at 20J, or
- Conversion of two consecutive episodes of SSVA at 30J in final system configuration.

Notes:

- In one of the two consecutive SSVA episodes, up to two 30J shocks are permitted.
- To achieve final system configuration, changing the position of the ICD generator and/or the lead or changing shock polarity is permitted.
- Subjects can return for testing on another day if testing is not fully completed on the day of implant.

The pre-specified OPC for this objective is 0.88 (88%), meaning the lower confidence bound of a two-sided 95% confidence interval for the proportion of EV ICD pts who achieve defibrillation testing success at implant must exceed 0.88.

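### The 6-month defibrillation result is described as meeting the primary 0.88 OPC on a point estimate in 17–34 subjects, with no interval planned and on a different test

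*SAP*

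**What the plan says.** Ancillary Objective #7 characterizes defibrillation testing success at 6 months. SAP 7.9.9.1 is explicit: "No statistical hypotheses will be tested for this objective". SAP 7.9.9.3 plans for a minimum of 17 and a maximum of 34 completed tests. SAP 7.9.9.2 nevertheless sets a performance requirement, namely that the observed proportion of subjects "for whom the episode is successfully terminated with a shock is at least 0.88". It then defines the endpoint as successful completion of the chronic testing protocol. SAP 7.9.9.4 assesses chronic efficacy "as defined by an observed chronic defibrillation success rate meeting the primary efficacy Objective Performance Criterion of 0.88". Protocol 12.12.2 and 12.12.4 carry the same requirement and the same label. SAP 7.9.9.5 names counts and percentages and no confidence interval.

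SAP 7.9.2.2 explains what the 0.88 OPC requires for the primary efficacy objective, "meaning the lower confidence bound of a two-sided 95% confidence interval" for the implant success proportion that must lie above 0.88. SAP 7.9.2.4 names the Clopper-Pearson method for it.

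**The concern.** The same named criterion is attached to two rules. At implant, meeting the OPC means that a rate of 0.88 or lower has been ruled out at one-sided 0.025. At 6 months, it means that the point estimate is no lower than 0.88. A report that follows SAP 7.9.9.4 faithfully could say that chronic efficacy met the primary OPC, on a small sample, without a measure of precision, and on a test that is not the one the OPC was set for. What is at stake is how the ancillary result is labelled and read; the primary objectives are not.

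**Working it through.** **1. The plan's own figure.** Inputs from SAP 6.2: N = 292, null rate 0.88, assumed true rate 0.935, reject at 268 or more successes, actual alpha 0.0243, beta 0.0981. The exact binomial tail P(X ≥ 268 | 292, p) is 0.0245 at p = 0.88 and 0.9015 at p = 0.935. With the finite population of 100,000 printed in the output, the hypergeometric tail gives 0.0243 and 0.9019 (beta 0.0981), which matches. The Clopper-Pearson lower limit is 88.02% at 268/292 and 87.62% at 267/292. The primary rule therefore needs an observed rate of 268/292 = 91.8%. A bare observed rule at the same size would need only 257/292 (0.88 × 292 = 256.96).

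**2. The chronic rule.** For each n from 17 to 34, take k as the smallest count with k/n ≥ 0.88. The Clopper-Pearson limits are the 0.025 quantile of Beta(k, n−k+1) and the 0.975 quantile of Beta(k+1, n−k). The chance of meeting the rule at true rate p is P(X ≥ k | n, p). The documents give no expected chronic rate: 0.935 is the plan's implant assumption, and the other rates are illustrative.

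| n | k | observed | exact 95% CI | chance at 0.80 | at 0.88 | at 0.935 |
|---|---|---|---|---|---|---|
| 17 | 15 | 88.2% | 63.6–98.5% | 31.0% | 66.5% | 90.6% |
| 25 | 22 | 88.0% | 68.8–97.5% | 23.4% | 64.8% | 92.4% |
| 33 | 30 | 90.9% | 75.7–98.1% | 8.1% | 42.9% | 83.6% |
| 34 | 30 | 88.2% | 72.5–96.7% | 16.2% | 61.2% | 93.3% |

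Over every n from 17 to 34, the lower limit at the smallest qualifying count runs from 63.6% to 75.7%. The chance of meeting the rule is 8–31% at a true 0.80, 43–67% at 0.88 and 80–93% at 0.935. It moves unevenly with n because k is a whole number.

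**3. The primary rule at these sample sizes.** With all n subjects successful, the lower limit is 0.025^(1/n): 87.7% at n = 28 and 88.1% at n = 29. So the rule cannot be met at n = 17–28, and at n = 29–34 it needs a perfect score (33/34 gives 84.7%). This shows how far apart the two rules are. It is not an argument for applying the primary rule here.

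**4. The two tests side by side.**

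- *Implant* (SAP 7.9.2.2; Protocol 8.5.7): one conversion at 20J, or two consecutive episodes converted at 30J. Testing "may require up to six successful SSVA episodes induced and up to 10 EV ICD shocks delivered", and "changing the position of the ICD generator and/or the lead, or changing shock polarity is permitted".
- *6 months* (Protocol Appendix I): at most two episodes and four shocks, programmed at 30J then 40J in Episode 1, and 40J then 40J in Episode 2. Any one conversion passes: "If Episode 2, Rx1 or Rx2 is successful in terminating the episode, the EV ICD System will have passed chronic defibrillation testing criteria". The device has "energy outputs as current transvenous systems (e.g., approximately 33cc and 40 Joules"), so a pass can come from a shock near its stated output.
- *Population*: subjects who fail implant testing have the system explanted and are exited (Protocol 8.5.8), so those tested at 6 months have passed at implant.

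The energies allowed make the chronic test more lenient; the number of attempts and the repositioning allowed make the implant test more lenient.

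**The case against.** The strongest reply is that the label is already qualified. SAP 7.9.9.2 and 7.9.9.4 both say that the rate is observed, no hypothesis is tested, and the small sample is explained by the burden on subjects. On that reading the plan borrows the number 0.88 and states its own rule, and a misleading report would have to drop the qualifier. Much of this stands, and it is why the point is minor. It does not remove the difficulty that SAP 7.9.9.4 speaks of meeting a named criterion which SAP 7.9.2.2 ties to a lower confidence limit.

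A second reply is that the missing interval is a matter of preference: readers can compute one from the counts, SAP section 3 allows further analyses, and most ancillary objectives name none. But Objective #7 is the only ancillary objective with a numerical performance requirement, and the hypothesis-free ATP objective does plan a 95% interval (SAP 7.9.7.4). Permission to add an analysis is not a plan to do so.

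Three stronger readings are tempting and not supported:

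- *The 6-month test is biased towards success.* The differences run both ways and the documents allow no net direction to be shown. The protocol is openly published, and 40J is also the therapy energy required at discharge (Protocol 8.6, Table 6).
- *The endpoint can be scored two ways, with opposite answers.* The singular reference to an episode in SAP 7.9.9.2 is loose. However, the same section defines the endpoint as completing the protocol successfully, and Appendix I passes a subject on either episode. No passage limits success to the first.
- *Spontaneous VF episodes inflate the proportion.* SAP 7.9.9.2 restricts it to induced episodes and SAP 7.9.9.5 summarizes spontaneous ones separately. Only the undivided list in SAP 7.9.9.6 is untidy.

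**Conclusion.** The concern holds as a matter of labelling and precision, and is worth considering rather than essential. An observed rate of at least 0.88 in 17–34 subjects is compatible with a true rate well below the OPC: the lower 95% limit at the smallest qualifying count is 63.6–75.7%. If the true rate were exactly 0.88, the observed rule would be met 43–67% of the time, against about 2.4% for the primary rule at 292 subjects. The intervals depend only on the counts and the exact method; the probabilities depend on assumed true rates. A reader might infer that the trial has a second, weaker route to its primary efficacy claim. The documents do not support that: the primary analysis is separate, Objective #7 tests nothing, and no primary conclusion or error rate is affected.

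**What to change.** (a) In SAP 7.9.9.5, report the protocol pass rate with a two-sided 95% Clopper-Pearson interval.

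(b) In SAP 7.9.9.2 and 7.9.9.4, state that 0.88 is a descriptive point-estimate benchmark, on a different test from the one at implant and in subjects who passed implant testing, and that reaching it does not show that the primary OPC is met. The same wording stands in the Protocol, so record in SAP 7.12 and in the clinical study report that this departs from Protocol 12.12.2 and 12.12.4. Protocol 12.1 requires an amendment only when a principal feature changes, and sends other analysis changes to the clinical study report.

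Editorial only: align the singular episode in SAP 7.9.9.2 with the stated endpoint (passing the chronic protocol in either episode), and say in SAP 7.9.9.6 that subjects with spontaneous VF enter only the separate summary.

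The cost is a few sentences and one interval, with no new testing and no change to the procedure. The primary lower-limit rule should not be imposed here, since it cannot be met below 29 subjects. The downside is that the ancillary result will look less definite.
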